## **11.6 POSTOPERATIVE PROCEDURES**

Postoperatively, subjects will be examined according to the schedule in Section 11.2, Visit Schedule. All subjects will be examined at the 1- and 6-month study visits. If a subject requires a lens repositioning procedure due to IOL misalignment or if a subject reports a severe visual distortion at 6 months, the subject will also undergo a final visit at 1 year.

At the 1-month visit, a spectacle and/or contact lens prescription will be offered to each subject. Postoperative procedures will include uncorrected and best corrected visual acuities, manifest refraction, intraocular pressure and biomicroscopic slit-lamp examination. In addition, if the subject has a spontaneous report of any of the 5 visual distortion items of interest or of blurred or hazy vision, the questionnaire will be administered and keratometry and toric IOL axis measurements will be performed.

Primary 6-month postoperative data collection consists of administration of a subject questionnaire for determination of visual distortion reports, manifest refraction, distance visual acuities, intraocular pressure, keratometry, and a biomicroscopic slit-lamp exam for determination of toric IOL axis position and for any adverse events.

If outside of a scheduled study visit, a subject has a spontaneous report of; 1) any of the 5 visual distortion items of interest or 2) blurred or hazy vision at one month postoperatively or later, the PRVDQ questionnaire will be administered and keratometry and toric IOL axis measurements will be performed. Exam details will be documented on an unscheduled visit form.

If a subject reports a severe visual distortion or has experienced a serious or device-related adverse event at any unscheduled study visit, uncorrected distance visual acuity, best corrected distance visual acuity, manifest refraction, keratometry, intraocular pressure and biomicroscopic slit-lam examinations will be performed.

Subjects should be assessed at each visit for occurrence of and/or change in status of any adverse events, particularly serious and/or device-related adverse events. If a serious or device-related adverse event occurs, details of the event are to be captured on an adverse event CRF and the exam details are to be captured on the appropriate visit CRF (i.e., 1-month, 6-month, 1-year or unscheduled). The event will be followed up as necessary and details captured on adverse event follow-up CRFs until resolution.

See Section 12.0, Adverse Events, and **Appendix D** Adverse Event Reporting Instructions, for further information.

If a serious or device-related adverse event occurs at or prior to the 6-month visit, details of the event will be collected at the time of the event using an adverse event form. If the adverse event results in an IOL repositioning procedure due to misalignment, the questionnaire should be administered prior to the procedure to collect information regarding visual distortions. Keratometry and toric IOL axis measurements will be performed prior to the repositioning procedure to collect data regarding the IOL misalignment.

If correction is required during the study postoperatively, spectacles or contact lenses will be prescribed; however, no additional refractive procedures (LRI, AK, etc.) are allowed until after completion of the 6-month study visit. If a subject is required to return for a 1-year exam (due to a severe visual distortion at 6 months or an IOL repositioning procedure during the study), a refractive enhancement (LRI, AK, etc.) may be performed prior to the 1-year exam but must be reported on the 1-year case report form; this enhancement will not be considered a secondary surgical intervention at this time.

The postoperative case report form will include the following information (Appendix A):

- Confirmation of offering of spectacle and/or contact lens prescription: 1-month visit only
- Questionnaire: (Following completion of the questionnaire by the subject, the questionnaire is to be reviewed by the site personnel for reports of severe visual distortions), 6-month and 1-year visits and also at 1-month or unscheduled visits only

if there is a spontaneous report of visual distortion or prior to an IOL repositioning procedure at that visit.

- Keratometry: 6-month and 1-year visits; also at 1-month and unscheduled visits if there is a spontaneous report of visual distortion or prior to an IOL repositioning procedure at that visit.
- Monocular uncorrected distance visual acuity, Snellen: all scheduled postoperative visits and unscheduled visits if a severe visual distortion or a serious or device-related adverse event is reported at that visit.
- Binocular uncorrected distance visual acuity, Snellen: 1- month, 6-month and 1-year visits; also at unscheduled visits if a severe visual distortion or a serious or device-related adverse event is reported at that visit.
- Manifest refraction (Snellen): 1- month, 6-month and 1-year visits; also at unscheduled visits if a severe visual distortion or a serious or device-related adverse event is reported at that visit.
- Monocular best corrected distance visual acuity, Snellen: 1- month, 6-month and 1-year visits; also at unscheduled visits if a severe visual distortion or a serious or device-related adverse event is reported at that visit.
- Binocular best corrected distance visual acuity, Snellen: 1- month, 6-month and 1-year visits; also at unscheduled visits if a severe visual distortion or a serious or device-related adverse event is reported at that visit.
- Toric IOL axis measurement by dilated slit-lamp examination (Refer to Appendix B for measurement instructions): 6-month and 1-year visits; also at 1-month and unscheduled visits if there is a spontaneous report of visual distortion or prior to an IOL repositioning procedure at that visit.
- Medical and lens findings from biomicroscopic slit-lamp exam: 1- month, 6-month and 1-year visits; also at unscheduled visits if a severe visual distortion or a serious or device-related adverse event is reported at that visit. Findings of aqueous cells and flare, corneal edema, posterior capsule striae, posterior capsular opacification and IOL glistenings are to be rated using a standardized grading scales provided in Appendix C.
- Ocular medications
- Intraocular pressure
- Dilated fundus exam, if medically indicated
- Occurrence of Nd:YAG capsulotomy(ies)
- Occurrence of any adverse events

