**11.5 OPERATIVE PROCEDURES**

The investigator should use his or her standard, small-incision, phacoemulsification, cataract extraction surgical technique. Lenses should be folded for implantation and inserted into the capsular bag using one of the AMO-validated insertion systems. **No additional refractive procedures are to be performed during the operative**

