**procedure or throughout the postoperative study period (e.g., LRI, OCCI, CRI, AK, PRK, LASIK or LASEK).**

Following lens insertion, the TECNIS Toric 1-Piece IOL is to be precisely aligned with the intended axis of placement using the imaginary line formed by the axis orientation marks at each of the haptic/optic junctions of the IOL, identifying the flat meridian of the optic. Carefully remove all viscoelastic from the capsular bag. Special care should be taken to ensure proper positioning of the TECNIS Toric IOL at the intended axis following viscoelastic removal and/or inflation of the capsular bag at the end of the surgical case. Residual viscoelastic and/or over-inflation of the bag may allow the lens to rotate, causing misalignment of the TECNIS Toric IOL from the intended axis.

Operative case report forms will include the following information:

- Date of surgery
- Operative eye
- IOL model, power and serial number
- Incision location
- Surgical complications
- Other surgical procedures
- IOL placement (e.g., within capsular bag, proper alignment, etc.)
- Wound closure (e.g., suture required)
- Adverse events

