### **Study-Specific Serious Anticipated Adverse Events**

The following is a list including, but not limited to, ocular adverse events that are anticipated and must be reported to AMO for this study. Any events that are unlikely but anticipated (i.e., endophthalmitis) will be reported to the FDA and other appropriate regulatory agencies.

- Endophthalmitis/Intraocular infection
- Hypopyon
- Hyphema
- IOL dislocation
- Cystoid macular edema
- Pupillary block
- Retinal detachment/tear
- Persistent corneal edema
- Persistent iritis
- Persistent raised IOP requiring treatment
- Axis misalignment requiring secondary surgical intervention (e.g., repositioning)
- Tilt and decentration requiring secondary surgical intervention (e.g., repositioning)
- Residual refractive error resulting in a secondary surgical intervention
- Residual lens remnants resulting in a secondary surgical intervention
- Visual symptoms requiring secondary surgical intervention

**NOTE 1:** Wound burps during the first week postoperatively, suture removal, planned blepharoplasty and Nd:YAG capsulotomy (for PCO) are not considered adverse events for this study.

**NOTE 2:** Raised IOP requiring treatment, cornea edema, and iritis will only be considered serious if persistent at the final study visit (120-180 days postoperative) or sight-threatening at the time of occurrence. Treatment merely to hasten the resolution of such conditions (and not intended to prevent permanent damage to the eye) will not be reported as serious adverse events.

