#### **6. One Year Data:**

Visual distortion findings, adverse events and medical/lens findings at one year will be reported for subjects who experienced a repositioning procedure during the study or for subjects who were reported with severe visual distortions at the 6-month visit.

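### Protocol 11.5 bars refractive procedures for the whole postoperative study period while 11.6 permits an enhancement before the 1-year exam, and the SAP reports the 1-year findings without showing who had one

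*Protocol*

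**What the plan says.** **The bar.** Protocol 11.5 says: "No additional refractive procedures are to be performed during the operative", and the same sentence continues "procedure or throughout the postoperative study period (e.g., LRI, OCCI, CRI, AK, PRK, LASIK or LASEK". It states no exception and does not refer to 11.6.

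**The permission.** Protocol 11.6 says that "no additional refractive procedures (LRI, AK, etc.) are allowed until after completion of the 6-month study visit". For subjects who must return at 1 year, because of a severe distortion at 6 months or an IOL repositioning, it then says that "a refractive enhancement (LRI, AK, etc.) may be performed prior to the 1-year exam but must be reported on the 1-year case report form".

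**The classification.** The same sentence of 11.6 ends: "this enhancement will not be considered a secondary surgical intervention at this time". Protocol 12.1 lists among the serious anticipated adverse events "Residual refractive error resulting in a secondary surgical intervention", with a parallel item for visual symptoms that need such an intervention.

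**The analysis.** SAP Section 6 says: "Visual distortion findings, adverse events and medical/lens findings at one year will be reported" for the repositioned and severe-distortion subjects. Protocol 20.4 says much the same. Neither mentions enhancement. SAP 4.4 counts adverse events at any postoperative time, so the period after 6 months is included.

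**The concern.** There are three linked problems.

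1. **Two rules.** A site that follows 11.5 would refuse an enhancement at, say, 8 months. A site that follows 11.6 could perform one. Each could cite the protocol, and the first could record the second's action as a deviation.

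2. **An unlabelled procedure.** The 1-year visit is the only scheduled follow-up of subjects with severe distortion at 6 months, and the permission is given to exactly the subjects who return for it. If a distortion has gone by 1 year, the cause could be time, adaptation or a corneal procedure. Without the enhancement status, a reader of the 1-year results cannot tell. For repositioning, Protocol 11.6 and 11.7 require the questionnaire, keratometry and axis measurement beforehand. No equivalent is stated before an enhancement.

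3. **A possible undercount.** If an enhancement done for residual error or visual symptoms is by definition not a secondary surgical intervention, the two 12.1 items that depend on that term are not triggered by it. The subject may then appear among those with no intervention.

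**Working it through.** **Step 1. Is the 1-year subject inside the postoperative study period?**

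- For: the Synopsis gives the duration as 6 months but follows these subjects through 1 year. Table 4 in Protocol 11.2 lists the 1-year exam as Visit 4. Protocol 11.6 calls it a final visit.
- Against: Note 2 in Protocol 12.1 describes the 120-180 day visit as the final study visit.

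For the subjects concerned, the first group of passages is specific and the Note is general. They are still in the study when 11.6 lets them have an enhancement, and 11.5 on its face forbids it. No passage reconciles the two.

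**Step 2. Do 11.6 and 12.1 conflict?** Section 12.1 makes residual refractive error or visual symptoms serious when they lead to a secondary surgical intervention. Section 11.6 takes the enhancement out of that term. Both sentences can be obeyed together, so this is a definition that narrows the list and not a logical contradiction. Its effect is to remove one route to a serious classification.

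**Step 3. What is still captured?** Protocol 12.3 requires all adverse events to be reported and recorded, whatever their severity or attribution. The general seriousness criteria in 12.1 apply independently of the label. Section 11.6 puts the enhancement on the 1-year case report form. The data exist; what is missing is a rule for showing them.

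**Step 4. How large is the 1-year set?** Inputs from Protocol 20.6 and SAP Section 7: N = 80, rate 0.025, 95% interval, half-width 0.05, stated probability 86%.

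- The plan's own figure: with an exact (Clopper-Pearson) interval and n = 80, the half-width is 0.0490 at 3 events and 0.0547 at 4, so the target is met with 3 or fewer. P(X <= 3 | 80, 0.025) = 0.8594, which reproduces 86%.
- Expected severe subjects: 80 x 0.025 = 2.0. The 97.5th percentile is 5, and P(none) = 0.975^80 = 0.13.
- With the 10% loss that Protocol 11.8 allows for: 72 x 0.025 = 1.8.
- At the 10% limit of the clinical hypothesis: 80 x 0.10 = 8.0, with a 95% range of 3 to 14.
- Repositioned subjects add to this. The documents give no rate for them.

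**Step 5. What can one enhancement do?** This is an illustration. It assumes that every severe subject would still be severe at 1 year without enhancement, and that the one enhanced subject resolves.

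| Severe subjects at 6 months | Still severe at 1 year, none enhanced | Still severe, one enhanced |
|---|---|---|
| 2 | 2/2 = 100% | 1/2 = 50% (exact 95% CI 1% to 99%) |
| 4 | 4/4 = 100% | 3/4 = 75% |
| 8 | 8/8 = 100% | 7/8 = 87.5% |

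**Step 6. What does not move?** Both rules bar enhancement until the 6-month visit is complete, so the primary endpoint, its interval and the 86% are unchanged. The named intervention endpoint in Protocol 6.2 is repositioning for misalignment. A corneal enhancement would not enter it under either rule.

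**The case against.** The strongest reply is that 11.5 gives the general rule and 11.6 a specific exception, with the study period understood to end at 6 months for most subjects. That is a fair way to read the intent. It still leaves an unqualified sentence in 11.5, and the Synopsis and Table 4 support the opposite reading for the affected subjects.

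It can also be said that the SAP plans no persistence estimate at 1 year. Section 6 says only that findings will be reported, Appendix I lists no 1-year table, and a subject-level listing of severe distortions is planned. This stands: with about two subjects, results may well be shown case by case. But the items named for that listing do not include enhancement.

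Three stronger readings are tempting, and the documents do not support them:

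- A reader might infer that 11.6 contradicts the 12.1 list, so that events vanish from the serious count. Section 11.6 sets a definition, and the reporting rules in 12.1 and 12.3 and the 1-year form still capture the event and the procedure.
- A reader might infer that the intervention endpoint mixes treated and untreated subjects. The only named one is repositioning, which an enhancement does not enter.
- A reader might put one enhanced subject at 20% to 33% of the 1-year set. That takes 2 severe plus an assumed 1 to 3 repositioned subjects (1/5 to 1/3). The assumed number has no source in the documents, and the ratio mixes repositioned subjects into a question about severe distortion.

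**Conclusion.** The point holds in a limited form. Protocol 11.5 and 11.6 state different rules for subjects who are still in the study, and they must be reconciled. The classification in 11.6 may produce an undercount of serious events in the any-time adverse event table; 11.6 and 12.1 should be reconciled on this.

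The effect is confined to the descriptive 1-year set and to adverse event counts after 6 months. At the planning rate that set holds about 2 severe subjects (about 8 at a 10% rate), plus an unknown number of repositioned subjects. In a set of 2, one unlabelled enhancement could change the reading from all persisting to half persisting. This rests on two assumptions: that someone chooses an optional procedure, and that it resolves the distortion. The study's main conclusion at 6 months does not depend on any of this. The change is worth making because it is cheap and keeps the few 1-year outcomes interpretable.

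**What to change.** 1. **Protocol.** Reconcile 11.5, 11.6 and the serious anticipated event list in 12.1, so that they state one rule on refractive procedures after the 6-month visit and one classification of an enhancement. The content of the rule is for the sponsor to decide.
2. **SAP Section 6.** Report 1-year distortion findings with each subject's enhancement status shown. With so few subjects, a flag in a listing is enough; a with/without split would also serve.
3. **SAP adverse event reporting.** Give the number of enhancements on a separate line beside the secondary surgical interventions, so that they are visible under either classification.

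The cost is some protocol wording and one more column or line in a small table. No new data are needed, because 11.6 already requires the enhancement on the 1-year case report form.

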## 11.7 UNSCHEDULED VISITS

A visit is considered an unscheduled study visit when it occurs other than at the specified 1- or 6-month study visits AND at which a serious or device-related adverse event is reported OR if the subject has a spontaneous report of any of the 5 visual distortion items of interest (lines that slant, tilt or separate, flat surfaces appearing curved, objects appearing further away or closer than they actually are, objects appearing to have a different size or shape, or physical discomfort related to vision as defined in Section 6.1) or of blurred or hazy vision at 1 month postoperatively or later.

For example, if the subject is seen for a routine (non-study) 3-month follow-up visit and there are no serious or device-related adverse events or any spontaneous report of visual distortion(s) of interest or of blurred or hazy vision at 1 month postoperatively or later, this would NOT be captured on an unscheduled visit form. If however, the subject commented on a visual distortion as listed above or a serious or device-related adverse event was noted at this visit, this visit would be captured on an unscheduled visit form. If a subject reports a visual distortion at an unscheduled visit, the PRVDQ questionnaire is to be administered, and keratometry and toric IOL axis measurements are to be performed.

If the subject reported a severe visual distortion in the questionnaire or if a serious or device-related adverse event was reported at any unscheduled visit, uncorrected and best corrected visual acuities, manifest refraction, keratometry, intraocular pressure and biomicroscopic slit-lamp examinations will be performed. If the event results in an IOL repositioning procedure (secondary surgical procedure), the PRVDQ questionnaire is to be administered and keratometry and toric IOL axis measurements are to be performed PRIOR to the IOL repositioning procedure for evaluation of visual distortions arising from IOL misalignment.

Data to be collected on unscheduled visit forms (due to serious or device-related adverse event or spontaneous report of visual distortion) include, as applicable:

- Questionnaire - in the event of a spontaneous report of visual distortion or prior to an IOL repositioning procedure
- Snellen manifest refraction
- Uncorrected and best corrected distance visual acuity using Snellen
- Intraocular pressure
- Slit-lamp examination for medical and/or lens findings
- Keratometry
- Toric IOL axis measurement
- Dilated fundus exam, if medically indicated
- Ocular symptoms
- Adverse events
- Medications

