#### SUBJECT DISCONTINUATION

Subjects will be discontinued from the study if the study lens is removed or if the subject dies. Subjects will be considered "lost-to-follow-up" from the study only if irretrievably lost for unavoidable reasons such as: subject moved/unable to locate, subject uncooperative/refuses further study participation, subject ill/unable to travel. The site shall document at least three attempts (phone calls/emails and/or letters) to locate lost-to-follow-up subjects and the investigator should notify AMO prior to exiting a subject from the study. If a subject is exited from the study, the investigator will, if at all possible, have the subject return for a final study visit. In the event of subject relocation, efforts must be made by the investigator to secure follow-up information (i.e., slit-lamp findings and general visual acuity, etc.) from the subject's new physician.

If a subject is exited early from the study, the investigator will complete an Exit Case Report Form indicating the reason for study exit. In the event of a lens removal or other serious adverse event, the subject may be exited from the study; however, efforts must be made by the investigator to follow the subject until resolution of the adverse event.

Note: A subject may be exited from the study if complications occur during the first-eye surgery and the planned study lens is not implanted; however, the eye will be followed until the resolution of the complication prior to exiting the subject from the study. If a complication occurs during the second-eye surgery and the planned study lens is not implanted in the second eye, the subject is to be followed according to the protocol for

the first eye (although data may be analyzed separately), and the second eye will be followed for safety until resolution of the complication.

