### 20.2 ANALYSIS POPULATION

For the primary endpoint and most visual distortion endpoints, the primary analysis population will be all bilaterally implanted subjects having available data at the 6-month visit. Data will also be reported for all subjects including bilateral subjects and those with only one eye implanted (having a phakic lens, a cataract or other IOL in the fellow eye). Data will also be reported by IOL group. If a subject does not have overall severe visual distortion data available at the 6-month visit (or had a repositioning procedure or IOL removal performed) then data for this endpoint will be carried forward from the most recent visit (for general missing data) or the visit with data taken prior to the IOL

repositioning or removal. If a subject had an IOL repositioning/removal and no questionnaire data prior to the procedure, then the subject will be considered to have had a severe visual distortion for this endpoint. An additional analysis will be performed for the primary endpoint using multiple imputation techniques for those with no questionnaire data available. Sensitivity analyses such as worst-case and best-case will also be performed.

Refraction, visual acuity, medical/lens findings, axis evaluation and adverse events will be reported for primary eyes (those having the higher cylinder IOL or the first eye implanted if the same IOL is implanted in both eyes) and fellow eyes. Data will be reported separately for ZCT450-ZCT600 eyes and ZCT 300-ZCT400 eyes.

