## APPENDIX A SUMMARY OF PROCEDURES REQUIRED AT EACH VISIT

Examination	Preoperative Both eyes	Op 1 1 st eye	Op 2 2 nd eye	Unscheduled Visit	1 Month Both eyes	6 Months Both eyes	1 Year a Both eyes
X = To be performed							
A = To be performed if a visual distortion is spontaneously reported prior to 6 month exam or prior to a required IOL repositioning (adverse event)							
B =To be performed if a subject reports a severe visual distortion or experiences a serious or device-related adverse event at this visit.							
O = Only if medically indicated							
Ocular history, inclusion/exclusion criteria	X						
Informed consent	X						
Potential visual acuity	X						
Targeted refraction/Targeted cylinder/IOL power calculations b /axial length	X						
Lens power/serial number/operative procedures		X	X				
UCDVA-photopic, monocular (Snellen)	X			B	X	X	X
UCDVA-photopic, binocular (Snellen)				B	X	X	X
Manifest refraction (Snellen)	X			B	X	X	X
BCDVA-photopic, monocular (Snellen)	X			B	X	X	X
BCDVA-photopic, binocular (Snellen)				B	X	X	X
Offer spectacle and/or contact lens prescription					X		
Keratometry	X			A/B	A	X	X
Intraocular pressure	X			B	X	X	X
Biomicroscopic slit-lamp exam c	X			B	X	X	X
Toric IOL axis measurement at dilated slit-lamp exam				A	A	X	X
Dilated fundus exam	X			O	O	O	O
Adverse events		X	X	X	X	X	X
Ocular medications	X			X	X	X	X
Subject questionnaire	X			A	A	X	X

a Examination at 1 year is to be conducted ONLY if a subject reported a severe visual distortion at 6 months or if the subject experienced an IOL repositioning procedure (due to IOL misalignment) during the study.

b Includes documentation of toric IOL calculations showing chosen ZCT for each eye and targeted cylinder outcome

c Includes determination of medical and lens findings/complications, including lens rotation

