## 2. Analysis Populations and Data Conventions

### 2.1 Analysis Population

The primary analysis population will be all bilaterally implanted subjects having available data at the six month visit. In addition, data for severe visual distortions (based on the 5 defined items) will also be reported for all subjects including bilateral subjects and those with only one eye implanted and the fellow eye having phakic status, a cataract, or another IOL. If a subject does not have overall severe visual distortion data available at the six month visit (or had a repositioning procedure or IOL removal performed) then data for the endpoint will be carried forward from the most recent postoperative visit (for general missing data) or the postoperative visit prior to the IOL repositioning or removal. If a subject had an IOL repositioning/removal procedure and did not have visual distortion data available prior to the procedure, then the subject will be considered to have had severe visual distortions for the primary endpoint. For overall severe visual distortions based on the 5 defined items, an additional analysis population will be evaluated that includes all subjects with last observation carried forward for missing data as described above as well as use of data imputation for subjects with no available questionnaire data at any time point. Imputation for those with no questionnaire data will be performed using multiple imputation techniques as described in Little and Rubin and implemented using the MI and MIANALYZE procedures in SAS® (Version 9.2 or later

version if available). Additional sensitivity analyses will be performed including worst-case analysis where all missing visual distortion data (using the 5 defined items) will be treated as having a severe visual distortion and best-case analysis where missing data is treated as having no severe visual distortion. If more than 10 percent of visual distortion data (using the 5 defined items) are missing then a tipping point analysis will also be evaluated.

Data will typically be reported for all bilateral subjects, however, for some analyses, such as the overall visual distortion endpoint, data will also be reported by IOL group. Subjects who have a lower cylinder IOL in one eye (e.g. ZCT300) and a higher cylinder IOL in the fellow eye (e.g. ZCT450) will be placed in the higher cylinder group for analysis when reporting data by subject.

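### A lens removal with no earlier questionnaire is scored as a severe visual distortion, but the procedure-based questionnaire and axis triggers name repositioning only

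*Protocol*

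**What the plan says.** **Scoring.** The default in Protocol 20.2 begins "If a subject had an IOL repositioning/removal and no questionnaire data prior to the procedure, then the subject will be considered", and it goes on to count that subject as severe. SAP 2.1 applies the same default to a subject who "did not have visual distortion data available prior to the procedure, then the subject will be considered to have had severe visual distortions". Neither asks why the lens was removed. For subjects who do have data, the SAP takes the value "carried forward from the most recent postoperative visit (for general missing data) or the postoperative visit prior to the IOL repositioning or removal".

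**Collection.** The triggers tied to a procedure are:

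- Protocol 11.6, and the matching sentence in 11.1: "If the adverse event results in an IOL repositioning procedure due to misalignment, the questionnaire should be administered prior to the procedure".
- The case report form list in 11.6, for the questionnaire, keratometry and axis measurement at 1-month and unscheduled visits: "if there is a spontaneous report of visual distortion or prior to an IOL repositioning procedure at that visit".
- Protocol 11.7, for unscheduled visits: "Questionnaire - in the event of a spontaneous report of visual distortion or prior to an IOL repositioning procedure".
- Appendix A, code A: "To be performed if a visual distortion is spontaneously reported prior to 6 month exam or prior to a required IOL repositioning (adverse event").

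The questionnaire is also given to every subject before surgery and at 6 months. From 1 month on, a spontaneous report of blurred or hazy vision triggers it as well (11.1, 11.6, 11.7).

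**Exit.** Protocol 11.8 says: "Subjects will be discontinued from the study if the study lens is removed or if the subject dies".

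**The concern.** The scoring rule needs a questionnaire before a removal, and no instruction tells the site to obtain one. Protocol 12.1 lists intraocular infection, and residual refractive error leading to further surgery, among the anticipated serious events, so a removal unrelated to distortion is foreseeable. A site that follows the protocol exactly could then add to the primary rate a severe distortion that no subject reported.

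The same eye may be lost to the misalignment analysis in SAP 4.2. That analysis needs the axis marker location, which cannot be read once the lens is out.

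**Working it through.** **1. Which subject is affected?** All four conditions must hold:

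- Both eyes received a study lens, so the subject is in the bilateral population.
- A lens is removed before the 6-month questionnaire. A later removal already has 6-month data.
- The subject has not volunteered one of the five distortion items, or blurred or hazy vision from 1 month on.
- There was no earlier repositioning that would have prompted a questionnaire.

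Such a subject has no postoperative questionnaire. Section 11.8 asks for a final visit at exit where possible, but answers given after the removal do not satisfy a rule that needs data from before it.

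**2. How is that subject scored?** Every subject has a preoperative questionnaire (Protocol 11.3, Appendix A), so the result depends on which earlier data count.

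| Reading | Result |
|---|---|
| Only postoperative data count | Default applies: severe |
| Protocol 20.2 read literally | A preoperative answer is earlier data, so the default is not met and that answer could be carried forward |
| SAP 2.1 read literally | The default is not met if the preoperative answer counts as available, yet carry-forward is limited to postoperative visits: no value assigned |

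The SAP's carry-forward wording favours the first reading, but neither default clause contains the word postoperative.

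**3. Which measurements are missing?** Keratometry is already required at an unscheduled visit with a serious or device-related adverse event (11.1, 11.7; code A/B in Appendix A). Axis measurement at such a visit has code A only. Section 11.7 includes it in a list to be collected as applicable, which does not require it before a removal.

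**4. The planned precision.** Inputs from Protocol 20.6 and SAP 7: n = 80, rate 0.025, target half-width 0.05, stated probability 86%. The interval method is not named. With the Clopper-Pearson 95% interval, the lower limit is the 0.025 quantile of Beta(x, n − x + 1) and the upper limit is the 0.975 quantile of Beta(x + 1, n − x):

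| Events | Rate | 95% interval | Half-width |
|---|---|---|---|
| 2 | 2.50% | 0.3% to 8.7% | 0.042 |
| 3 | 3.75% | 0.8% to 10.6% | 0.049 |
| 4 | 5.00% | 1.4% to 12.3% | 0.055 |

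The target is met for x ≤ 3. For X ~ Bin(80, 0.025), P(X ≤ 3) = 0.8594, which reproduces the stated 86%.

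**5. Effect of default-scored removals.** The number k is not in the documents; 0, 1 or 2 is assumed. Each adds 1/80 = 1.25 points. With the other 80 − k subjects at 2.5%, the probability of meeting the half-width is P(X ≤ 3 − k) for X ~ Bin(80 − k, 0.025):

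- k = 0: 0.859
- k = 1: 0.684
- k = 2: 0.416

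**6. Does the upper limit pass 10%?** For 3/80 it is 10.6% by Clopper-Pearson. By continuity-corrected Wald, which also reproduces 86%, it is 0.0375 + 1.96 × √(0.0375 × 0.9625/80) + 1/160 = 0.0375 + 0.0416 + 0.0063 = 0.0854, or about 8.5%. Plain Wald gives 7.9%. The crossing depends on the method.

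**The case against.** The strongest reply is that the default is deliberate, conservative and stated in advance. Counting an unassessed removal against the device is defensible in a post-approval safety study. The SAP's table listing also includes a listing of subjects with severe distortions, and SAP 2.1 reports adverse events with the lens implanted, so a careful reader could largely identify such a subject. This stands as a reason to keep the default for gaps that cannot be avoided. It does not justify a gap that a change of trigger wording would close. The worst-case and best-case analyses do not clearly help, because SAP 2.1 does not say whether a default-scored removal counts as missing there.

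Three stronger readings are tempting, and the documents do not support them.

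- *A reader might infer that the questionnaire is given only before a repositioning.* Spontaneous reports of a distortion item, or of blurred or hazy vision from 1 month, also trigger it. A subject facing removal for residual refractive error could well volunteer blur.
- *A reader might infer that every unrelated removal becomes severe.* The default is conditional, and it depends on excluding the preoperative questionnaire, which neither default clause does expressly.
- *A reader might infer that keratometry is lost too.* It is already required where the removal follows a serious or device-related event seen at an unscheduled visit.

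It is also fair to say that a removal for acute infection may allow no questionnaire, so that subject could still be scored as severe after the change.

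**Conclusion.** The mismatch is real but narrow. The scoring rule covers removal for any cause; the procedure-based triggers for the questionnaire and the axis reading cover repositioning only. Where the four conditions hold and the default means postoperative data, the plan scores as severe a subject who reported nothing. If the preoperative questionnaire counts, the two documents can give the same subject different values, which also needs settling.

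Each such subject adds 1.25 percentage points at n = 80, half of the assumed 2.5% rate. One lowers the probability of the planned half-width from 0.859 to 0.684 and two lower it to 0.416, with the exact interval. With no removals there is no effect, and the documents do not say how many to expect.

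A reader might infer that one such removal would defeat the clinical hypothesis of less than 10%. The documents do not support that. No rule compares the upper limit with 10%, SAP 4.1 describes the aim as estimating the rate, and 3/80 = 3.75% is itself below 10%.

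**What to change.** 1. In Protocol 11.1, 11.6, 11.7 and Appendix A code A, extend the questionnaire and the toric axis measurement to the time before any repositioning, exchange or removal of the lens, whatever the cause, where the subject's condition allows. Keratometry needs no new trigger at unscheduled visits with a serious or device-related event.
2. State in both Protocol 20.2 and SAP 2.1 that only postoperative questionnaire data count, for carry-forward and for the default.
3. Keep the default-to-severe rule only where the questionnaire could not be obtained. List those subjects with the reason for removal, and report the primary rate with and without them.

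The cost is a wording change in the two documents and the unscheduled-visit form, plus one existing questionnaire and one axis reading under dilation in a few subjects.
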